#### **10.1 Primary Efficacy Endpoint**

The primary endpoint, number of oocytes retrieved, will be compared between REKOVELLE and GONAL-F using a negative binomial regression model with treatment and AMH level at stimulation day 1 (AMH <15 pmol/L, AMH  $\geq$ 15 pmol/L, or missing) as factors. The absolute treatment difference in number of oocytes retrieved, the associated 95% confidence interval, and the p-value for no treatment difference will be derived from the model estimates using the delta method.

The distribution of the number of oocytes retrieved will be visualised in histograms. Furthermore, the number of oocytes will be grouped and presented in tables and figures using the following classification:

- <4 oocytes or cycle cancellation due to poor ovarian response
- 4-7 oocytes
- 8-14 oocytes
- 15-19 oocytes
- $\geq 20$  oocytes or cycle cancellation due to excessive ovarian response
- Cycle cancellation due to another reason than poor or excessive ovarian response

The treatment difference will also be investigated for sub-groups defined by AMH level at stimulation day 1 (i.e. <15 pmol/L, AMH  $\geq$ 15 pmol/L or missing) using the same methods as above for each sub-group separately.

No formal hypothesis testing will be conducted using these methods.

As a supplementary analysis, the analysis of the primary endpoint will be repeated using the PP analysis set and corresponding summary tables will be presented.

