#### **3.2** Planned Number of Trial Sites and Subjects

It is planned to randomise approximately 300 subjects from 15-20 sites in 3-6 European countries.

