### 4.2.2 Randomisation

On day 2-3 of the menstrual cycle, subjects will be randomised in a 2:1 ratio to treatment with either REKOVELLE or GONAL-F, and stimulation will be initiated. Randomisation is performed centrally through the IRT. The randomisation number will be allocated to the subject together with the treatment allocation. When a subject is randomised to the trial, she will always be assigned to the lowest available randomisation number. An independent statistician at the Ferring Global Biometrics Department will prepare a computer-generated randomisation list and randomisation is performed in blocks. Blocks will be maintained within trial sites, i.e. randomisation will be stratified by trial site. The block size will only be revealed when the trial database is declared clean and locked. An overview of recruitment will be recorded on a subject identification code list for all randomised subjects kept by the investigator.

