# 9.5 Trial Population

# Demographics and other Baseline Characteristics

Descriptive statistics of demographics and other baseline characteristics (body measurements, ultrasound parameters, endocrine parameters) will be presented for the FAS. A summary of demographic characteristics will be presented by trial site.

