# 9.7.2 Primary Endpoint

The primary endpoint, number of oocytes retrieved, will be compared between REKOVELLE and GONAL-F using a negative binomial model with treatment and AMH level at stimulation day 1 (AMH <15 pmol/L, AMH  $\geq$ 15 pmol/L, or missing) as factors. The absolute treatment difference in number of oocytes retrieved, the associated 95% confidence interval, and the p-value for no treatment difference will be derived from the model estimates using the delta method.

The distribution of the number of oocytes retrieved will be described using kernel estimates. Furthermore, the ovarian response will be grouped according to the following classification:

- <4 oocytes or cycle cancellation due to poor ovarian response
- 4-7 oocytes
- 8-14 oocytes
- 15-19 oocytes
- $\geq 20$  oocytes or cycle cancellation due to excessive ovarian response
- Cycle cancellation due to another reason than poor or excessive ovarian response

The treatment difference will also be investigated for the two sub-groups AMH <15 pmol/L and AMH  $\geq$ 15 pmol/L using the same methods as above.

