#### **3.2** Determination of Sample Size

In a previous trial (MERIT), 347 subjects aged 22-37 years were treated with a starting dose of 225 IU GONAL-F. In these subjects the mean number of oocytes retrieved was 11.8 and the standard deviation was 5.7. Assuming that the standard deviation for number of oocytes retrieved in this trial will be 6.0, a total sample size of 300 with a 2:1 randomisation will give a 2-sided 95% confidence interval ranging from -1.44 to +1.44 oocytes from the observed difference. This level of precision is considered as sufficient and is also more precise than the equivalence limits of  $\pm 3$  oocytes that has been applied in previous trials comparing biosimilar FSH compounds.

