#### 10 EFFICACY

Unless otherwise specified, analyses of efficacy endpoints will be based on the FAS and summary tables for the primary and secondary efficacy endpoints will be presented in total and by treatment group. Continuous variables will be presented with number of subjects, mean, standard deviation, median, inter-quartile range, minimum, and maximum. Categorical variables will be presented with number and percentage of subjects within each specific category.

Results of statistical analyses will be based on least-squares means using the observed margins and include the estimated treatment difference (or ratio), a 95% confidence interval for the difference (or ratio), and the p-value for the test of no treatment difference. All analyses are of descriptive nature and no adjustments for multiple tests will be applied.

Missing observations for the endpoints number of oocytes retrieved, number of fertilised oocytes, and number of blastocysts will be replaced with zero (i.e. worst-case imputation technique) irrespective of the reason why data is not recorded. For pregnancy data, lack of data will be interpreted as a negative pregnancy.

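### Randomisation is stratified by site but the primary negative binomial model omits site; if site is prognostic after AMH, the reported 95% CI is modestly too wide

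*Combined protocol and SAP*

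**What the plan says.** Protocol 4.2.2 states: "Blocks will be maintained within trial sites, i.e. randomisation will be stratified by trial site". Protocol 3.2 gives the scale: "It is planned to randomise approximately 300 subjects from 15-20 sites in 3-6 European countries", which is 300/20 = 15 to 300/15 = 20 subjects per site on average.

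The primary analysis has the same terms throughout. Protocol 9.7.2 (and the synopsis) compares the arms "using a negative binomial model with treatment and AMH level at stimulation day 1", and SAP 10.1 does so "using a negative binomial regression model with treatment and AMH level at stimulation day 1". AMH is classed as below 15 pmol/L, 15 pmol/L or above, or missing. The absolute difference and its 95% CI come from the model by the delta method. SAP 10 adds: "Results of statistical analyses will be based on least-squares means using the observed margins". It also sets unrecorded counts to zero whatever the reason: "Missing observations for the endpoints number of oocytes retrieved, number of fertilised oocytes, and number of blastocysts will be replaced with zero".

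No endpoint analysis uses site. The only by-site summary is in Protocol 9.5: "A summary of demographic characteristics will be presented by trial site". SAP 13 lists no site-related change, and the only supplementary analysis of the primary endpoint is the per-protocol repeat.

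SAP 3.2 justifies the sample size by precision alone: 300 subjects "will give a 2-sided 95% confidence interval ranging from -1.44 to +1.44 oocytes from the observed difference". SAP 10.1 plans no formal hypothesis test.

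**The concern.** The factor used to stratify the randomisation is missing from the analysis, while AMH, which was not stratified on, is in it. With allocation balanced inside each site, differences between sites largely cancel from the treatment contrast. The true sampling error then depends mainly on variation within sites. A model without site puts the between-site variation into the dispersion parameter and so into the standard error, and no robust or re-randomisation variance is planned to take it out again.

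A site effect is plausible but not shown. Dose adjustment (Protocol 6.2.2) and cycle cancellation (Protocol 6.2.3) both rest partly on the investigator's judgement.

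At stake is the calibration of the interval. With no formal test, and a sample size justified by CI width, the interval is the trial's main result and should reflect the design that was used.

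**Working it through.** **The plan's own figure.** SD 6.0, 200 and 100 subjects (SAP 3.2):

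1.96 × 6.0 × √(1/200 + 1/100) = 1.96 × 6.0 × 0.1225 = 1.440. The stated 1.44 reproduces.

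**Linear approximation.** If site explains a share ρ of the variance and allocation is balanced within site, the true half-width is 1.44 × √(1 − ρ), and a model without site is too wide by the factor 1/√(1 − ρ).

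| ρ | True half-width | Too wide by | Coverage without site |
|---|---|---|---|
| 5% | 1.40 | 2.6% | 95.6% |
| 10% | 1.37 | 5.4% | 96.1% |
| 15% | 1.33 | 8.5% | 96.7% |

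**Simulation of the planned model.**

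- From the documents: 300 subjects, 2:1 allocation, blocks within site, mean 11.8, SD 6.0, model terms, observed margins, delta method.
- Assumed: 18 sites (within the planned 15-20) of 33, 29, 28, 25, 23, 22, 20, 19, 17, 16, 14, 12, 11, 10, 8, 6, 4 and 3 subjects; blocks of 3; half the subjects with AMH of 15 pmol/L or above; rate ratio 1.5 between AMH classes; no missing AMH; true difference 0; zeroed cycles independent of site and arm.
- AMH: the class means are 9.44 and 14.16, so AMH contributes 2.36² = 5.57 of 36 (15.5%) and leaves 30.43.
- Site: a share ρ of 30.43 needs a log-scale site variance s² = ln(1 + ρ × 30.43/144.8), where 144.8 = 11.8² + 5.57. This gives s = 0.102, 0.144 and 0.176 for ρ = 5%, 10% and 15%.
- Dispersion before zeros: a₀ = ((1 − ρ) × 30.43 − 11.8)/(144.8 × exp(s²)). With zero share z, a = (1 − z)a₀ − z, which keeps the overall mean at 11.8 and SD at 6.0.
- Fits: (1) the SAP model by maximum likelihood; (2) the same with a random site intercept (21-point Gauss-Hermite quadrature), the difference multiplied by exp(σ²/2), and fallback to (1) if the estimated site SD is below 0.005.
- Size: 6,000 trials per cell, so Monte Carlo error is about 0.9% on an SD and 0.3 points on coverage. Half-width is 1.96 × mean SE.

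No zeroed cycles (SAP model / random site intercept):

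| Site share | Half-width | Narrowing | Mean SE / actual SD | Coverage | Fallback used |
|---|---|---|---|---|---|
| 0% | 1.310 / 1.307 | 0.2% | 0.993 / 0.991 | 94.9% / 94.9% | 63% |
| 5% | 1.306 / 1.280 | 2.0% | 1.020 / 1.003 | 95.1% / 94.7% | 9.9% |
| 10% | 1.301 / 1.245 | 4.3% | 1.039 / 0.998 | 95.7% / 94.9% | 1.5% |
| 15% | 1.295 / 1.210 | 6.6% | 1.048 / 0.985 | 96.1% / 94.5% | 0.3% |

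In oocytes the narrowing is 0.00, 0.03, 0.06 and 0.08. The actual SD of the estimate hardly moves (0.639 against 0.637 at 10%), so the gain is in the reported width only. A separately coded repeat with 500 trials per cell gave half-widths of 1.310, 1.307, 1.299 and 1.293 against 1.307, 1.280, 1.244 and 1.209.

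**Cycles set to zero.** The zero rule can itself make the negative binomial interval conservative, so its part was separated (SAP model / random site intercept):

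| Site share | SE/SD, 2% zeros | Narrowing | SE/SD, 5% zeros | Narrowing | Coverage, 5% zeros |
|---|---|---|---|---|---|
| 0% | 1.019 / 1.016 | 0.2% | 1.084 / 1.083 | 0.1% | 96.3% / 96.3% |
| 5% | 1.035 / 1.015 | 1.9% | 1.142 / 1.121 | 1.6% | 97.6% / 97.2% |
| 10% | 1.078 / 1.035 | 4.1% | 1.152 / 1.107 | 3.7% | 97.5% / 97.0% |
| 15% | 1.075 / 1.008 | 6.5% | 1.195 / 1.120 | 6.1% | 97.7% / 96.9% |

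At 5% zeros most of the excess width is not due to site and stays after adjustment.

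**Fixed site terms.** A separate simulation (18 sites, complete blocks, mean 11, 2,000 trials per scenario) fitted all site terms as fixed. Coverage was 93.7% to 94.4%. At site log-SDs of 0.10, 0.15 and 0.20 the model SE was 0.625, 0.602 and 0.572 against actual SDs of 0.641, 0.622 and 0.596. Part of that apparent narrowing is not real.

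**The case against.** The strongest reply is that no defect has been demonstrated for this trial. The between-site variance is unknown. The protocol also limits it, with a fixed starting dose, bounded adjustment steps, a common triggering criterion and a common retrieval rule. At a 5% share, coverage is 95.1%, so there is nothing to see. Any error is in the safe direction, the analyses are labelled descriptive, and no margin is set that 0.03 to 0.08 oocytes could cross. A simple model that matches the protocol is defensible. The replacement depends on the data through its fallback, and it must state how the difference is averaged over sites: leaving out exp(σ²/2) shifts the estimate by 0.5% to 1.6% at the site SDs simulated. On this view a stated reason or a site-adjusted sensitivity analysis would be enough.

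Most of the facts here stand: the size is unknown and probably small, the direction is conservative, and the estimator itself gains almost no precision. They do not remove the point. The protocol's standardisation limits site differences without excluding them. The averaging rule can be written in one line. When site has no effect, the fallback left coverage the same for both models. A sensitivity analysis alone would show the problem but leave the main interval out of step with the randomisation.

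**Conclusion.** The concern holds, in a conditional and modest form. Site is stratified on and then left out of the primary model without explanation. If site explains 5% to 15% of the variance left after AMH, the reported interval could be about 2% to 7% narrower. If site explains none, nothing is lost by the current model. The figures rest on assumed site share, site sizes, block size (which the protocol deliberately withholds), AMH split and AMH effect. Less complete blocks at small sites would reduce the excess width. There is no bias and no type I error inflation, and the sample-size statement is correct. Excess width from cycles set to zero is a separate matter. Only the primary endpoint was examined.

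**What to change.** Before unblinding:

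- Add site as a random intercept to the primary negative binomial model, alongside treatment and AMH class.
- Derive the absolute difference at the observed margins, averaged over sites by the multiplier exp(σ²/2), with the delta method for the CI. Write the multiplier into the SAP.
- Pre-specify the fallback: if the site variance is estimated as zero or the fit does not converge, report the current treatment and AMH model.
- Keep the current model as a sensitivity analysis.
- Do not use fixed site terms for this purpose, because they slightly under-cover under maximum likelihood.
- List the change and its reason in SAP Section 13, where SAP 1 says main changes are described.

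The cost is a few lines of SAP text, one Section 13 entry and one extra model fit. There is no gain if site is not prognostic: the fallback then applied in 63% of simulated trials (80% with 5% zeros). The change does not address excess width caused by the zero rule, and it is not a request to alter the secondary analyses.

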### NUMBER OF SUBJECTS

The total number of subjects to be randomised is approximately 300, i.e. 200 randomised to treatment with REKOVELLE and 100 randomised to treatment with GONAL-F.

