# 9 STATISTICAL METHODS

# 9.1 Justification of Sample Size

In a previous trial (MERIT), 347 subjects aged 22-37 years were treated with a starting dose of 225 IU GONAL-F. In these subjects the mean number of oocytes retrieved was 11.8 and the standard deviation was 5.7. Assuming that the standard deviation for number of oocytes retrieved in this trial will be 6.0, a total sample size of 300 with a 2:1 randomisation will give a 2-sided 95% confidence interval ranging from -1.44 to +1.44 oocytes from the observed difference. This level of precision is considered as sufficient and is also more precise than the equivalence limits of  $\pm 3$  oocytes that has been applied in previous trials comparing biosimilar FSH compounds.

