#### Pregnancy

For subjects with a clinical pregnancy (at least one gestational sac 5-6 weeks after transfer), the type of clinical pregnancy (intrauterine or ectopic) will be described. For subjects with a vital pregnancy (at least one intrauterine gestational sac with fetal heart beat 5-6 weeks after transfer), the number of intrauterine gestational sacs with fetal heart beat will also be described.

Pregnancy rates in the first transfer cycle will be compared between treatments using a logistic regression model with treatment and age group (<35, 35-37, or 38-40 years) as factors. The estimated probabilities, difference in probabilities and 95% CIs for the estimated difference in probabilities will be presented based on the delta method. In these analyses subjects with no transfer or missing data on pregnancy will be regarded as non-pregnant.

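### Age is left out of the primary oocyte model although it is collected and used elsewhere in the plan; adding it may narrow the interval modestly at little cost

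*Combined protocol and SAP*

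**What the plan says.** Protocol 9.7.2 compares oocytes retrieved "using a negative binomial model with treatment and AMH level at stimulation day 1", and SAP 10.1 does so "using a negative binomial regression model with treatment and AMH level at stimulation day 1". AMH has three levels in both: below 15 pmol/L, 15 pmol/L or above, and missing. Neither text has an age term or gives a reason for leaving it out. The same model serves follicle counts, fertilised oocytes and blastocyst counts (SAP 10.2).

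Age is used elsewhere. SAP 7.1.1 tabulates it in years and in three bands (<35, 35-37, 38-40). SAP 10.4 says: "Pregnancy rates in the first transfer cycle will be compared between treatments using a logistic regression model with treatment and age group". The implantation model also carries age group.

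On planning, protocol 9.1 relies on a trial in which "347 subjects aged 22-37 years were treated with a starting dose of 225 IU GONAL-F". SAP 3.2 reports that in those women "the mean number of oocytes retrieved was 11.8 and the standard deviation was 5.7", and then assumes that "the standard deviation for number of oocytes retrieved in this trial will be 6.0". Inclusion criterion 3 admits women from 18 to 40 years. Randomisation is stratified by site only (protocol 4.2.2).

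**The concern.** The trial sets no power and no margin of its own, and SAP 10.1 says there will be no formal test. Its one stated performance figure is the width of the confidence interval for the difference in oocytes, so precision is the design target. A baseline variable that predicts the outcome can narrow that interval without extra subjects.

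Age is a natural candidate. It has to be known at randomisation to check eligibility, so it should be available even for women whose AMH is missing. The sponsor already treats it as prognostic for pregnancy and implantation. A two-way split of AMH is also a coarse summary of ovarian reserve and could leave age-related variation in the residual. At stake is a possible small gain in precision on the primary endpoint and on the count endpoints that reuse its model.

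**Working it through.** **Inputs.** Arm sizes: "200 randomised to treatment with REKOVELLE and 100 randomised to treatment with GONAL-F" (synopsis, number of subjects). SD 6.0 and two-sided 95% confidence (SAP 3.2). The share of variance that age explains beyond treatment and AMH category, R², is not in the documents and is assumed.

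**Step 1: reproduce the plan's figure.** SAP 3.2 states that "a total sample size of 300 with a 2:1 randomisation will give a 2-sided 95% confidence interval ranging from -1.44 to +1.44 oocytes". Half-width = 1.96 × 6.0 × √(1/200 + 1/100) = 1.440, which agrees. It uses the marginal SD, so it takes no credit for AMH or any other covariate and does not depend on age.

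**Step 2: the planning SD.** Moving from 5.7 to 6.0 raises the variance by the factor 6.0²/5.7² = 36/32.49 = 1.108, or about 11%. The documents do not say what this allowance is for.

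**Step 3: effect of an age term.** New half-width = old half-width × √(1 − R²). The proportional change applies to the planned model's half-width after AMH adjustment, whatever that is; 1.44 serves only as an illustrative base. Equivalent sample size without age = 300/(1 − R²).

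| Assumed R² | Half-width on base 1.44 | Reduction | Equivalent N |
|---|---|---|---|
| 0 | 1.440 | 0 | 300 |
| 0.01 | 1.433 | 0.007 | 303 |
| 0.02 | 1.426 | 0.014 | 306 |
| 0.05 | 1.404 | 0.036 | 316 |
| 0.10 | 1.366 | 0.074 | 333 |

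At R² = 0.10 the factor is √0.90 = 0.949, a reduction of about 5%.

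**Step 4: check in the planned model class.** Negative binomial data were simulated for 200 and 100 subjects, 400 runs per scenario. The assumptions were a mean near 11.8, an AMH effect of 0.5 on the log scale, a latent age-AMH correlation of −0.3 and dispersion 0.16. Each data set was fitted with and without continuous age, with delta-method intervals at the observed margins.

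| Assumed log effect per SD of age | Half-width without age | With age | Change |
|---|---|---|---|
| 0 | 1.355 | 1.355 | 0% |
| 0.05 | 1.373 | 1.364 | −0.7% |
| 0.10 | 1.385 | 1.354 | −2.2% |
| 0.15 | 1.425 | 1.355 | −4.9% |
| 0.20 | 1.465 | 1.344 | −8.3% |

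The simulated marginal SDs ran from 6.6 to 7.4, so only the within-row comparison is informative. Part of the narrowing is also a change of scale. Setting age at its mean on the log scale gives a fitted mean lower by up to about a factor exp(b²/2), which is exp(0.02) = 1.02 for b = 0.20. This is why the SAP has to say how age enters the margins.

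**Step 5: chance imbalance.** The standard error of the difference in mean age between arms is √(1/200 + 1/100) = 0.122 SD. A two-standard-error imbalance with an assumed 10% effect per SD would move the unadjusted estimate by about 0.245 × 0.10 × 11.8 = 0.29 oocytes; with a 5% effect, by 0.14. The interval's stated uncertainty already covers movement of this kind.

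**The case against.** The strongest reply is that the gain is asserted rather than shown. It needs age to predict oocyte number beyond AMH category, and neither document gives a figure for that. Use of age in the pregnancy and implantation models does not supply one, because those models have a different outcome and omit AMH. The plan follows a consistent pattern: AMH for ovarian-response endpoints, age for pregnancy endpoints. It calls ±1.44 sufficient, sets it beside ±3 from other trials, and describes its analyses as descriptive, so no decision turns on a few hundredths of an oocyte. The model is also fixed in the protocol, so changing it is a change to the primary analysis.

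Most of this stands. It limits the point to a possible gain that may be zero. It does not remove the case for the change: an age term showed no loss in the simulation when age was irrelevant, and a narrower interval when it was not.

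A reader might go further and infer that women aged 38-40 bring variation that the planning SD left out, or that omitting age does widen the interval. The documents support neither. The SD was raised from 5.7 to 6.0 without a stated reason, so it cannot be shown that the wider age range was overlooked, and the age-oocyte association is not given. A reader might also infer bias from uncorrected age imbalance. Age is not a randomisation stratum, and chance imbalance is part of sampling error.

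**Conclusion.** This is an optional efficiency improvement. The primary model is valid as written, and its stated precision is reproduced without age. Precision may be left unused: for an assumed R² of 0-10% after AMH, the half-width would shrink by 0-5%, at most about 0.07 oocytes on a base of 1.44, equivalent to up to about 33 additional subjects. The size rests wholly on that assumed range, and zero is within it.

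**What to change.** Before unblinding, amend SAP 10.1 to add age at randomisation to the primary negative binomial model, either as a continuous term or in the existing bands <35, 35-37 and 38-40. Make the same change in the follicle, fertilised-oocyte and blastocyst models that reuse it. The AMH subgroup analyses use the same methods, so say whether age carries over to them.

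SAP section 10 bases results on least-squares means at observed margins. If age is continuous, state whether predictions are averaged over the subjects in the full analysis set or evaluated at mean age, since on the log scale these give different absolute differences. List the change in SAP section 13.

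If the sponsor prefers to keep the protocol's primary model, a prespecified age-adjusted sensitivity analysis, or a sentence justifying the omission, would be a weaker alternative.

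The cost is one extra model term (two parameters if banded), a few SAP sentences and a documented departure from the protocol analysis. A continuous term also assumes a log-linear age effect, which the bands avoid. No new data are needed.

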#### 6.2 Stimulation

#### 6.2.1 Start of Stimulation – Day 1

Subjects will attend the stimulation day 1 visit on day 2-3 of the menstrual cycle.

The following must take place before administration of the first IMP dose:

- Ensure that the subject is still eligible for participation in the trial
- Check those inclusion and exclusion criteria that were not possible during screening
- Urinary pregnancy test must be negative
- Transvaginal ultrasound of ovaries (number and size of follicles)
- Blood collection for central laboratory analysis of endocrine parameters (AMH, estradiol, and progesterone)

<sup>d Alternatively, age may be recorded in case country-specific restrictions do not permit recording the full date of birth.

• Blood collection for potential future biomarkers (*applicable for subjects who have provided additional, optional consent*)

If the subject fulfils all inclusion and exclusion criteria, she will proceed to randomisation:

• Randomisation, i.e. assignment to the lowest available subject number and thereby allocation to either REKOVELLE or GONAL-F

Once the above has been completed, the following must be performed by the trial medication delegate. Care must be taken to ensure blinding of the investigator and other assessors.

• Dispensing of IMP according to randomisation and instruct the subject on how to administer the IMP. The subject will self-administer the IMP (at the trial site) as a subcutaneous injection in the lower part of the abdomen. The IMP starting dose of 15  $\mu$ g/day with REKOVELLE or 225 IU/day with GONAL-F must be maintained for at least 4 days.

Finally, this must be done before the subject leaves the clinic:

- Recording of use of any concomitant medication
- Recording of adverse events

The IMP should preferably be administered at the same time each day during the stimulation period (with the possible exception of stimulation day 1).

# 6.2.2 Start of GnRH Antagonist – Day 5 or Day 6

The following must take place on stimulation day 5 or day 6:

- Dispensing of IMP
- Evaluation of potential dose adjustments based on the subject's response
- Implementation of dose adjustments, if applicable
   The daily REKOVELLE dose can be increased or decreased by 5 µg based on the subject's
   response. The minimum REKOVELLE dose is 5 µg and the maximum REKOVELLE dose
   is 20 µg. The daily GONAL-F dose may be adjusted by 75 IU based on the subject's

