#### 7.1.3 Endocrine Parameters

The following endocrine parameters measured at stimulation day 1 will be tabulated: AMH (pmol/L), AHM category (<15 pmol/L,  $\geq$ 15 pmol/L, missing), progesterone (nmol/L) and estradiol (pmol/L).

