#### Number of Follicles at End-of-stimulation

The follicle cohort at end-of-stimulation (EOS) will be summarised by treatment on the subject level (i.e. total number of follicles, and number of follicles  $\geq 10 \text{ mm}$ ,  $\geq 12 \text{ mm}$ ,  $\geq 15 \text{ mm}$  and  $\geq 17 \text{ mm}$ ). Additionally, the mean number of follicles  $\geq 10 \text{ mm}$ ,  $\geq 12 \text{ mm}$ ,  $\geq 15 \text{ mm}$  and  $\geq 17 \text{ mm}$  at EOS will (in separate analyses) be compared between treatments using the same negative binomial regression model as used for the primary endpoint.

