# Number of Fertilised Oocytes and Fertilisation Rate

An oocyte is defined as correctly fertilised if it is scored as 2 pronuclei (PN) on day 1 after oocyte retrieval. The mean number of correctly fertilised oocytes will be compared between treatments using the same analysis method as for the primary endpoint.

For subjects with >0 oocytes retrieved, the rate of correctly fertilised oocytes to oocytes retrieved will be estimated and compared between treatments using a negative binomial regression model with treatment and AMH level at stimulation day 1 (AMH <15 pmol/L, AMH  $\ge$ 15 pmol/L, or missing) as factors and the number of retrieved oocytes (log-transformed) as an offset. The treatment difference in fertilisation rate and the associated 95% confidence interval will be derived using the delta method.

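### Minor precision gain, not an error: the primary model uses measured baseline AMH only in groups; adding log(AMH) to the existing factor could narrow the interval by up to about 7% at almost no cost

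*Combined protocol and SAP*

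**What the plan says.** Protocol section 9.7.2 specifies a "negative binomial model with treatment and AMH level at stimulation day 1 (AMH <15 pmol/L", and SAP section 10.1 keeps it as a "negative binomial regression model with treatment and AMH level at stimulation day 1 (AMH <15 pmol/L". In both, the remaining levels are 15 pmol/L or above, and missing. The absolute difference and its 95% interval come from the delta method. SAP section 10 bases results on least-squares means at the observed margins.

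The concentration itself is available. Protocol section 6.2.1 lists, before the first dose, "Blood collection for central laboratory analysis of endocrine parameters (AMH, estradiol, and progesterone". SAP section 7.1.3 has "endocrine parameters measured at stimulation day 1 will be tabulated: AMH (pmol/L" alongside the category.

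Other count endpoints borrow the primary model. Follicle counts use the same "regression model as used for the primary endpoint", fertilised oocytes are compared "using the same analysis method as for the primary endpoint", and blastocysts are handled likewise (all SAP section 10.2).

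For estradiol and progesterone, SAP section 10.2 enters the log-transformed day-1 concentration as a continuous covariate and sets values below the LLOQ to LLOQ/2. AMH is not treated that way, and no reason is given. Randomisation is stratified by site only (protocol section 4.2.2), so the design does not force the grouping.

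**The concern.** A two-group split keeps only part of what a continuous prognostic variable can explain. If oocyte count rises with AMH inside the two groups, the planned model leaves that variation in the residual and the interval is wider than it need be.

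This is relevant because the sample size is justified by interval half-width alone (SAP section 3.2), and the estimated difference with its interval is the main result. The gain would come from data already collected, with no extra subjects.

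The stakes are small. SAP section 10 states: "All analyses are of descriptive nature and no adjustments for multiple tests will be applied". No decision rule depends on the interval.

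**Working it through.** **Inputs from the documents.** SD 6.0, 300 subjects at 2:1 (200 and 100), two-sided 95% interval; mean of 11.8 in the previous trial (SAP section 3.2).

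**Assumed inputs, not in the documents.** Correlation r of log(AMH) with oocyte count, 0.3 to 0.5; share p of subjects below 15 pmol/L, 50% or 30%; the shape of the relation.

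**Step 1: the plan's figure.** 1.96 × 6.0 × √(1/200 + 1/100) = 1.440. The stated 1.44 reproduces. It takes no credit for any AMH adjustment.

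**Step 2: closed form, log-linear relation, normal log(AMH).** A cut with share p below it keeps φ(z_p)² / [p(1−p)] of the variance that log(AMH) explains: 0.637 at p = 50% and 0.576 at p = 30%. The half-width is 1.440 × √(1 − kept × r²) for the factor alone and 1.440 × √(1 − r²) once log(AMH) is in the model.

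| Share below 15 | r | Factor only | With log(AMH) | Narrowing |
|---|---|---|---|---|
| 50% | 0.3 | 1.398 | 1.374 | 1.7% |
| 50% | 0.4 | 1.365 | 1.320 | 3.3% |
| 50% | 0.5 | 1.321 | 1.247 | 5.6% |
| 30% | 0.3 | 1.402 | 1.374 | 2.0% |
| 30% | 0.4 | 1.372 | 1.320 | 3.8% |
| 30% | 0.5 | 1.333 | 1.247 | 6.4% |

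In oocytes, the gain in half-width runs from 1.398 − 1.374 = 0.02 to 1.333 − 1.247 = 0.09.

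**Step 3: simulation.** Negative binomial counts, mean 11.8, SD 6.0, 200 versus 100, with predictions averaged over subjects and delta-method intervals in every model.

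- Log-linear: adding log(AMH) to the factor narrows the interval by 1.7-7.4% for r of 0.3 to 0.5.
- Same slopes, flat beyond ±1 SD of log(AMH): about 0.3-2.5%.
- Flat beyond ±0.5 SD: essentially nothing.
- Pure step at the cut, 50% below it: adding log(AMH) leaves the half-width at 1.359 (R² = 0.1) and at 1.276 (R² = 0.2). Replacing the factor widens it to 1.384 and 1.335, that is by 1.8% and 4.6%.

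**Step 4: zero counts.** SAP section 10 sets unrecorded counts to zero "irrespective of the reason why data is not recorded". This was tested with 5% random zeros plus zeros in 20% of the top AMH decile (both assumed) and slopes set for r of 0.3 to 0.5. The factor-only interval was then only 0.3-1.7% wider than the log(AMH) interval at a median cut, and 0.4-2.1% wider at a 30% cut. This run used log(AMH) in place of the factor. Under a log-linear relation at R² = 0.2 the two forms gave the same half-width, 1.269.

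**Step 5: scale of the estimate.** With a log link, least-squares means at observed margins are evaluated at the mean log(AMH), which is not the average of predicted counts. At R² = 0.2 and a median cut, with log(AMH) replacing the factor, the apparent narrowing was 5.1% on that scale and 4.2% with averaged predictions. Part of the former is a change of scale.

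**The case against.** The strongest reply is that this is a modelling preference. The planned model needs no functional form and no LLOQ rule, keeps subjects with missing AMH without a fill, and matches the groups used throughout the SAP tables. The plan calls ±1.44 sufficient. All of that stands, and is why the point is optional.

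A second reply is that the AMH slope may be weak here. Doses may be adjusted to response from day 5 or 6 (protocol section 5.1.1). Women with previous exuberant response, OHSS or polycystic ovarian syndrome are excluded, as are those judged unsuitable for about 225 IU/day (section 4.1.2). These features could narrow the AMH range or flatten the relation. On the other side, the approved REKOVELLE regimen is itself based on AMH and body weight (section 1.1), while here everyone in an arm starts on one dose. AMH is therefore plausibly prognostic, but neither the size nor the shape of the relation is documented.

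A third reply is that a continuous term could do harm if the truth is a step at 15 pmol/L. That holds for replacing the factor; it does not hold for adding to it.

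A reader might also infer that the grouping biases the estimate or invalidates its interval. It does not: coarse coding of a pre-dose covariate in a randomised comparison costs efficiency, and simulated coverage of the planned model was 0.92-0.97. Nor does the grouping endanger ±1.44. At SD 6.0 the factor-only model already gives 1.32 to 1.40 in the table above. Both models exceed 1.44 only in the added-zeros setting, because the assumed zeros raise the SD to about 6.4.

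**Conclusion.** The point holds as a minor efficiency suggestion. The planned analysis is valid, and neither the sample size nor any conclusion depends on the coding. Adding log(AMH) to the existing factor would narrow the primary interval by about 2-7% under a log-linear relation with r of 0.3 to 0.5 and 30-50% of subjects below 15 pmol/L. The gain falls towards zero as the relation flattens, and under a step the interval changes by at most 0.1%. Every one of these inputs is assumed, so no single figure should be quoted as the expected gain. The calculations cover oocytes retrieved only.

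**What to change.** Before the blind is broken, amend SAP section 10.1 as follows.

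- Keep the three-level AMH factor and add log(AMH) as a continuous covariate.
- Set AMH below the LLOQ to LLOQ/2, as SAP section 10.2 already does for estradiol and progesterone. Give missing AMH a fixed fill value; the existing missing level then acts as the indicator, so the choice of fill does not affect the fit.
- Derive the absolute difference and its delta-method interval by averaging each subject's predicted counts under both treatments, in place of the observed-margins rule in SAP section 10.
- Keep the planned categorical model as a sensitivity analysis, with the difference derived in the same averaged way so that the two intervals are comparable. Keep the categorical approach for the AMH subgroup analyses.

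If the sponsor prefers to leave the primary model alone, the extended model can be prespecified as the sensitivity analysis instead. Extending the change to the follicle, fertilised-oocyte and blastocyst counts is optional, since no gain was computed for them.

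The cost is one extra parameter, a short amendment and modest programming. No new data are needed.
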